6.2. Secondary Objectives and Outcome Measures

Objective	Outcome Measures
To assess the cost- effectiveness of NMP in the context of NHS commissioning guidelines	 NMP versus SCS intervention costs NHS resource use, measured by documentation of inpatient and outpatient episodes and treatments at study timepoints, data collected for patients on the transplant waiting list, historically published data and hospital episode statistic (HES) data; valued using standard NHS unit costs Health-related quality of life for patients on the waiting list and post-transplant, assessed by completion of the EQ-5D-5L questionnaire
To assess biochemical liver function in the study cohort	 Daily serum bilirubin, GGT, ALT and INR at days 1-7 following transplantation. Daily serum lactate at days 1-7 whilst in high level (ITU/HDU) care Serum bilirubin, ALP, ALT and AST at month 12 following transplantation. Model for Early Allograft Function (MEAF) score (9): a composite score based upon the maximum values of ALT, INR and bilirubin during the first 3 days postoperatively.
To compare graft and patient survival between study and control cohorts	 Primary non-function: graft failure during the first 10 days after liver transplantation, documented by the site team as PNF with no initial function Graft survival (death censored) at 7 days, 3 and 12 months and 5 years following transplantation (defined as a functioning transplant in the absence of death and re-transplantation). Graft survival (non-censored) at 7 days, 3 and 12 months and 5 years following transplantation (graft loss includes death or retransplantation) Patient survival at 7 days, 3 and 12 months and 5 years following transplantation.
To compare the use of postoperative hospital	 Length of stay in high level (HDU/ITU) care post-transplant Length of initial hospital stay post-transplant

resource between study and control cohorts	Need for renal replacement therapy (haemodialysis, haemofiltration, haemodiafiltration)

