9.8. Subsequent Follow-up

9.8.1. Inpatient stay

Patients will be assessed daily by their clinical team and managed according to normal local protocols.

Outcome assessment

All investigations while an inpatient are performed as part of routine clinical care. No additional procedures are required as part of the study protocol while participants are inpatients.

The following biochemical outcomes will be collected as part of the study:

- Daily serum samples for the first 7 days post-transplant, to include:
 - Serum bilirubin (measured in μmol/l)
 - Serum gamma-glutamyl transferase (GGT; measured in IU/L)
 - Serum alanine transaminase (ALT; measured in IU/L)
 - International normalised ratio (INR)
- Daily serum lactate (measured in mmol/L) whilst on ITU/HDU.

The first measurements should be taken at 12 to 24 hours post-transplant. For subsequent measurements, in the event that more than one measurement is taken in a 24 hour period, the measurement taken closest to the specified follow-up time-point should be used.

Other outcomes include data routinely collected in the registry immediately post-transplant:

- Length of stay in ITU (days)
- Number of days ventilated
- Total length of hospital stay (days)
- Requirement for renal replacement therapy during transplant admission:
 - Transient renal filtration

Clinical Trial Protocol Template version 14.0

- Short-term dialysis
- Long-term dialysis
- Graft and patient survival at day 7 post-transplant
- Primary non-function: graft failure during the first 10 days after liver transplantation, documented by the site team as PNF with no initial function, as documented in the transplant registry.

Safety outcomes

These safety outcomes are data routinely collected in the registry immediately post-transplant:

- Recipient infection (defined as both clinically diagnosed treated infection and infection with a positive microbiological culture result):
 - o CMV infection
 - o Fungal infection
 - o Postoperative sepsis and site
- Biopsy-proven rejection episodes
- Biliary complications
 - Biliary tract strictures requiring intervention anastomotic and non-anastomotic. Defined as those requiring surgical or radiological intervention
 - Bile tract leaks. Defined as those requiring drainage, refashioning of anastomosis or stenting.
- Vascular complications
 - o Haemorrhage. Defined as bleeding requiring reoperation.

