Secondary outcomes will be presented using descriptive statistics and analysed using a similar approach, with adjustment for donor type and use of NRP. However, when performing analyses on the subset of transplanted livers, adjustment will also be made for the transplanting centre where numbers allow. General Linear and Generalised Linear Models or non-parametric methods will be used as appropriate for the different outcomes. Length of HDU/ITU and hospital stay post-transplant will be analysed using a competing risks approach where death is the competing risk. Measures of biochemical liver function at 12 months will be compared between the two treatment arms using linear regression, with appropriate transformation if required. Patient and graft survival (censored and non-censored) will be estimated using the Kaplan-Meier method and analysed using Cox Proportional Hazards regression. Safety outcomes will be summarised for each arm according to classification and severity. Some outcomes are only measured in the study arm and these will be presented using descriptive statistics. Measures of biochemical liver function over the first seven days will be presented graphically and area under the curve summarised for the study arm, along with a summary of the MEAF score.

During the trial, data will be collected regarding perfusion parameters (including machine logs and perfusate characteristics). These data will be analysed separately to the main clinical trial outcomes to explore relationships between perfusion parameters, utilisation and transplant outcomes.

Clinical Trial Protocol Template version 14.0

CONFIDENTIAL

© Copyright: The University of Oxford and Oxford University Hospitals NHS Foundation Trust 2018

After the final patient has reached five years post-transplant, patient and graft survival will be obtained from the transplant registry. The unadjusted survival rates at five years will be estimated using the Kaplan-Meier method. A Cox proportional hazards model will also be used to assess the treatment effect after risk-adjustment for any imbalance in baseline characteristics that is known to affect recipient outcome.

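### MEAF is defined on three-day maxima of ALT, INR and bilirubin, but the collection rule keeps one value per day from 12 hours onward, so the score can fall below its definition and never above it

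*Protocol*

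**What the plan says.** Section 6.2 lists MEAF under the secondary objective "To assess biochemical liver function in the study cohort" and defines it as "a composite score based upon the maximum values of ALT, INR and bilirubin during the first 3 days postoperatively".

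Section 9.8.1 governs how those results are collected:

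- Frequency: "Daily serum samples for the first 7 days post-transplant, to include" bilirubin, GGT, ALT and INR.
- Start: "The first measurements should be taken at 12 to 24 hours post-transplant".
- Several results in one day: after the first measurement, if a day yields two or more results, the rule is that "the measurement taken closest to the specified follow-up time-point should be used".
- Source: "All investigations while an inpatient are performed as part of routine clinical care".

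The schedule in Appendix 2 has one mark per analyte per day, D1 to D7, with no clock time. The registry items listed for the inpatient stay in sections 9.8.1 and 10.4.1 include no day 1-7 ALT, INR or bilirubin, so no second source is named. Section 13.2 plans "area under the curve summarised for the study arm, along with a summary of the MEAF score".

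**The concern.** A maximum and a nearest-to-time-point value are different statistics. The nearest-value rule suits a daily profile or an area under the curve, where evenly spaced values are wanted. It does not suit a maximum, because it selects by time and ignores the level. Results before 12 hours also lie outside the collection rule, although they lie inside the three-day window of the definition.

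The SAP can say how MEAF is calculated, but it cannot recover results that sites were told not to enter. At stake is a listed secondary outcome reported under a definition that its data may not meet, with an error that runs in one direction. Sampling frequency is left to routine care, so the error may also differ between recipients and centres.

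**Working it through.** The protocol gives no expected value, standard deviation or threshold for MEAF, so there is no figure to reproduce. The check has a logical part and an illustrative part.

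**1. Direction.** For one analyte in one recipient, let A be all routine results from 0 to 72 hours and R the results kept under section 9.8.1. R is a subset of A, so max(R) ≤ max(A). Equality holds when the highest result is itself retained. The inequality is strict when the highest result was taken before the first retained sample, or was a later same-day result not chosen. No recipient can have an error in the other direction, so averaging cannot remove it. Carrying this over to the score assumes that MEAF does not fall as a component rises; the protocol does not give the formula.

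**2. Where each loss arises.** The closest-value rule applies only to measurements after the first. On day 1 the loss comes from the 12 to 24 hour window; on days 2 and 3 it comes from the selection rule.

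**3. Chance of discarding a day's highest value.** If a day has m results in exchangeable order and one is kept, the highest is lost with probability 1 − 1/m:

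- m = 1: 0
- m = 2: 0.50
- m = 3: 0.67
- m = 4: 0.75

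**4. Illustrative size.** All inputs in this step are assumptions, not protocol figures. One analyte was simulated over 0-72 hours in 4,000 recipients per scenario.

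- Curve: linear rise to a peak, then exponential decay with a half-life of 24 hours (log-scale noise 5% or 15%) or 48 hours (noise 5%).
- Peak time: uniform over 2-12, 6-24, 12-36 or 24-48 hours.
- Retained: the first sample at 12-24 hours (if none, the sample nearest 18 hours), then on days 2 and 3 the sample closest to 24 and 48 hours after it.
- Result: highest retained value divided by highest value drawn. Mean shortfall = 1 − mean ratio.

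| Assumed sampling | Mean ratio, range over scenarios | Mean shortfall | Recipients whose highest value is lost |
|---|---|---|---|
| every 6 h | 0.818-0.924 | 7.6-18.2% | 65-81% |
| every 8 h | 0.845-0.931 | 6.9-15.5% | 51-73% |
| every 12 h | 0.848-0.955 | 4.5-15.2% | 32-56% |
| every 24 h | 0.968-1.00 | 0-3.2% | 0-9% |

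In round terms, the shortfall is 0-3% with one sample per day and 4-18% with sampling every 6 to 12 hours. These are shortfalls in one component's maximum, not in the MEAF score.

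**The case against.** The strongest reply is that section 6.2 lists daily ALT, INR and bilirubin just before MEAF, so the maximum may mean the highest of the daily values. On that reading there is no conflict. The reading is possible, but section 6.2 does not say it, and stating which reading applies would itself be a correction.

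A second reply is that section 9.8.1 does not mention MEAF, and that the SAP or eCRF specification may deal with its derivation. Derivation may well sit there. Collection is set in the protocol, however, and it names no other source for these results.

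A third reply is that daily sampling is the stated norm and several results in a day only a contingency. This stands: if recipients are sampled once a day, the loss is nil or small. The protocol does not say how often bloods are taken, or that sicker recipients are sampled more often.

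Three stronger readings are tempting but unsupported:

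- *That ALT is understated by 8-41%.* This follows if ALT is assumed to peak at 6 hours and to fall with a half-life of 24-48 hours: 2^(−6/48) = 0.92 at 12 hours and 2^(−18/24) = 0.59 at 24 hours. Neither the peak time nor the half-life is in the protocol. The calculation covers only the first sample, says nothing about the closest-value rule, and gives no start-window loss if the peak comes later.
- *That the rule makes NMP grafts look better than they are.* This needs a comparison with external MEAF values, and none is planned.
- *That it undermines the objective of predicting clinical outcomes from perfusion data.* The protocol does not name MEAF as the outcome for that objective.

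**Conclusion.** The mismatch between sections 6.2 and 9.8.1 is real. Each component maximum taken from the collected data equals or falls below the maximum in the definition. The direction is certain for the components, and holds for the score if it does not fall as a component rises. The size is not known: the 0-3% and 4-18% figures rest entirely on the assumed curve, peak times and sampling intervals.

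A reader might infer that MEAF cannot be computed as defined at all. That goes too far, because the definition is met in any recipient whose highest values happen to be retained, including many sampled once a day.

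The consequence is limited. MEAF is secondary, confined to the study arm and summarised descriptively. The primary analysis and all between-cohort comparisons are unaffected. The correction is still worth making because the error is one-directional and the remedy is simple.

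**What to change.** In section 9.8.1, state that for MEAF the highest ALT, INR and bilirubin from any routine sample between reperfusion and the end of day 3 is recorded from existing laboratory records. Keep the closest-value rule for the daily profiles and the 7-day area under the curve.

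Where peaks cannot be retrieved for recipients already followed, redefine and report the outcome as *MEAF from once-daily values*, note that it may understate the peak, and do not compare it with externally published MEAF values.

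The cost is three additional eCRF fields per recipient, a protocol amendment and record retrieval at the seven centres, with no extra sampling. Most of the retrieval would be retrospective: planned recruitment ended on 11/10/2023, and the latest version in the amendment history is dated 23/07/2024. If that effort is judged out of proportion for a descriptive outcome, relabelling alone would bring the definition and the data into agreement.

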9.9. Sample Handling

9.9.1. Routine sampling

All samples taken as part of routine care (donor and recipients) will be processed in local laboratories for clinical purposes as per normal protocols. For study purposes, the results of these investigations will be documented. These samples will be handled as per routine clinical practice.

9.9.2. Samples for central analyses

Optional perfusate samples and liver biopsy for central analyses will be collected in accordance with national regulations and requirements including standard operating procedures for logistics and infrastructure. Samples will be taken in appropriately licensed premises, stored and transported in accordance with the HTA guidelines and local trust policies. Samples for central analysis will be kept in the Oxford Radcliffe bioresource. The stored tissues will be held under an extension of the University of Oxford's HTA license (12217). Additional (optional) consent will be sought for long-term storage of these samples beyond the end of the study for use in future studies. Where consent is obtained, these samples will be stored in the Oxford Radcliffe bioresource under an extension of the University of Oxford's HTA license (12217). Where no consent for long-term storage is obtained, the samples will be destroyed at the end of the study.

9.10. Early Discontinuation/Withdrawal of Participants

All patients completing the 12-month follow-up assessment will be regarded as having completed the study. All patients will be encouraged to complete study follow-up, with letters sent to encourage completion of quality-of-life questionnaires. All reasonable efforts will be made to ensure completeness of follow-up, with central monitoring of registry returns and reminders to centres for timely submission.

Clinical Trial Protocol Template version 14.0

CONFIDENTIAL

Measures include ensuring that assessments are made at routine hospital visits, and that patients do not incur extra financial costs (e.g. travelling costs) as a result of study participation.

It is understood that study participants may withdraw consent for study participation at any time irrespective of their reasons. The investigators may also withdraw a recipient from the study in order to protect their safety and/or if they are unwilling or unable to comply with the required study procedures. We will keep all data accrued to the point of withdrawal, as is stipulated in the trial consent form.

Possible reasons for investigator-led withdrawal of a participant from the trial include:

- Ineligibility either arising during the trial or retrospectively having been unknown/overlooked at screening
- Withdrawal of consent
- Loss to follow-up

In the event of a patient withdrawing from the trial, the reason for withdrawal must be documented on the eCRF. Such patients will be asked whether they consent to the use of ongoing data collected as standard in the national transplant registry for the purposes of this study. If they do not consent to use of data collected, this will not be used in analysis.

9.11. Definition of End of Trial

Data will be collected from participants for 12 months post-transplant. Once all data from all participants has been collated, entered and cleaned, the database will be locked and the study will end. Longer-term (5-year) follow-up data (beyond the end of the study) will be collected from the UKTR.

10. DATA COLLECTION FOR RETROSPECTIVE CONTROL COHORT

10.1. Description of data

Outcome data for the retrospective control cohort will all be collected from the National Transplant Registry in an anonymised fashion. Outcomes will mirror those collected for the prospective study cohort, where possible, to allow direct comparison between cohorts. The data fields of the National Transplant Registry that are accessed for the purpose of this study are detailed in the PLUS Data Sources document. Registry data are collected at the time of registration, transplant, month 3 and month 12 post-transplant. Donor data are also available from the registry. These data will be used as the basis for the following assessments.

10.2. Baseline Assessments

10.2.1. Donor and Recipient Demographics

Donor and recipient demographics will be identical to those collected for the study cohort, as described in section 9.6.1, and 9.6.2.

10.3. Operative data

Donor timings

These are all routinely collected at the time of retrieval and will be obtained from the NHSBT database.

The parameters to be recorded include the same subset of parameters recorded for the prospective cohort described in 9.7.2:

- Timings:
 - Withdrawal of support (DCD donors only)
 - Onset of functional warm ischaemia (DCD donors only)
 - Cessation of donor circulation (asystole in DCD donors)
 - Start of cold perfusion
 - Liver removal from the donor (hepatectomy)
 - Liver packed for transport time
- Perfusion solution used for aortic perfusion
- Perfusion solution used for storage and transport
- Degree of steatosis (graded mild, moderate, severe) surgeon's assessment
- Quality of *in-situ* perfusion (graded poor, moderate, good)

Operative parameters

These will include the same subset of parameters collected for the prospective cohort and described in 9.7.2:

- Cold ischaemic time
- Veno-venous bypass time
- Operative reperfusion time
- Intraoperative transfusion of blood products measured in units.

10.4. Subsequent Follow-up

10.4.1. Month 3 data

Immediate post-transplant data that are also collected in the same way for the prospective cohort:

- Length of ITU stay (days)
- Number of days ventilated
- Total length of hospital stay (days)
- Requirement for renal replacement therapy during transplant admission
 - o Transient filtration
 - Short-term dialysis
 - o Long-term dialysis
- Graft and patient survival at day 7 post-transplant
- Primary non-function: graft failure during the first 10 days after liver transplantation, documented by the site team as PNF with no initial function, as documented in the registry.

Inpatient Safety Outcomes as recorded in the registry:

- Recipient infection (CMV infection, fungal infection, post-operative sepsis)
- Biliary complications
 - Biliary tract strictures requiring intervention
 - o Bile tract leaks requiring intervention.
- Vascular complications
 - o Haemorrhage. Defined as bleeding requiring reoperation
 - Hepatic artery thrombosis
 - o Portal vein thrombosis.
 - o IVC/Hepatic vein occlusion.

Month 3 outcomes:

- Graft and patient survival at month 3 post-transplant
- Lifestyle activity score (see Appendix 6)

Immunosuppression

Details of maintenance immunosuppression at 3 months post-transplant will be included as recorded in the registry.

Clinical Trial Protocol Template version 14.0

CONFIDENTIAL

© Copyright: The University of Oxford and Oxford University Hospitals NHS Foundation Trust 2018

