To assess the ability of perfusion parameters, biomarkers in perfusion fluids and graft histology to predict clinical outcomes following transplantation.	 Perfusion parameters (logged automatically by the device): a. Arterial and caval pressures (in mmHg) b. Arterial, portal and caval flow rates (in L/min) c. pO₂, pCO₂ and pH d. Blood temperature (°C), Glucose (mmol/L) and bile production (ml/h) Perfusate ALT at time zero, 2 and 4 hours, and the end of NMP Perfusate lactate at time zero, 15 min, 1, 2 and 4 hours, and end of NMP Note: time zero is when the liver is put onto the OrganOx metra Perfusate cell-free DNA (cfDNA) levels during perfusion at 2 and 4 hours Graft histology, including degree of macrosteatosis, following reperfusion
To assess safety in the study and control cohorts	 Organ discard rate Perfusate culture. At the end of preservation a sample will be taken for microbiological culture (NMP livers only). Adverse outcome rates. Severity will be graded according to the Clavien-Dindo classification for any reported as SAEs for the study cohort (10) Recipient infection Biopsy proven rejection Biliary complications (biliary strictures or bile duct leaks) requiring intervention Vascular complications requiring intervention (bleeding, hepatic artery stenosis, hepatic artery thrombosis, portal vein thrombosis, portal vein stenosis) Reoperation rate

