 - Hepatic artery thrombosis. Defined as formation of new clot resulting in graft dysfunction or loss, or requiring pharmacological, radiological or surgical intervention.
 - Portal vein thrombosis. Defined as formation of new clot resulting in graft dysfunction or loss, or requiring pharmacological, radiological or surgical intervention.
 - o IVC/hepatic vein occlusion. Defined as formation of new clot resulting in graft dysfunction or loss, or requiring pharmacological, radiological or surgical intervention.
- Reoperation rate

Severity for any adverse events reported as SAEs will be graded according to the Clavien-Dindo classification (10) – *Appendix 5*.

Immunosuppression

Details of induction immunosuppression and maintenance immunosuppression (including doses) at day 7 post-transplant will be recorded.

9.8.2. Month 3

For efficiency, the majority of 3-month data will be collected from the NHSBT transplant registry. As the only available outcome data for the RWC cohort will come from the registry, this will also ensure comparability between the control and study cohorts.

In addition to clinical data, patients will be asked to complete the EQ5D-5L quality of life questionnaire at 3 months. The quality of life questionnaire (EQ-5D-5L) will be delivered either during a routine hospital visit, or remotely via telephone or internet.

Outcome assessment

Outcomes to be included from routinely collected data in the registry:

- Graft and patient survival at month 3 post-transplant
- Lifestyle activity score (see Appendix 6)

Outcomes to be collected and which are not routinely collected data in the registry:

- Healthcare resource use (including days in ITU, days ventilated and length of initial hospital stay).
 Hospital Episode Statistic (HES) data linkage will be used as a backup to verify resource use.
- Quality of life (ED5D-5L questionnaire).

Safety outcomes

Safety outcomes that are not part of routine registry collection and will be collected for the study:

- Biopsy-proven rejection episodes and treatment
- Biliary complications
 - Biliary strictures anastomotic and non-anastomotic. Both radiologically diagnosed and clinically apparent strictures
 - Bile duct leaks. Defined as those requiring drainage, refashioning of anastomosis or stenting.
- Vascular complications
 - o Haemorrhage. Defined as bleeding requiring reoperation

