10.4.2. Month 12 data

Outcomes to be collected include:

- Graft and patient survival at month 12 post-transplant
- Number of readmissions in past 12 months (and reasons for readmission)
- Presence of transplant-related renal dysfunction
- Healthcare resource use in past 12 months (including inpatient days).
- Lifestyle activity score (see Appendix 6)

The following biochemical outcomes will be recorded at month 12 post-transplant:

- Serum bilirubin (measured in μmol/l)
- Serum alanine transaminase (ALT; measured in IU/L)
- Serum aspartate transaminase (AST; measured in IU/L)
- Serum alkaline phosphatase (ALP; measured in IU/L)
- Blood urea (mmol/L)
- Serum creatinine (μmol/l)

Immunosuppression

Details of maintenance immunosuppression at 12 months post-transplant will be recorded.

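### The 12-month adverse-outcome comparison planned for both cohorts cannot be made like for like, because controls have only inpatient registry complications

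*Protocol*

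**What the plan says.** **The comparison.** Section 6.2 has a safety objective covering both cohorts, with adverse outcome rates among its measures. It defines the biliary item as "Biliary complications (biliary strictures or bile duct leaks) requiring intervention". The synopsis gives that objective the timepoints days 1-7 and months 3 and 12. Section 13.2 compares NMP with the control cohort on all primary and secondary outcomes other than the 5-year ones, and adds: "Safety outcomes will be summarised for each arm according to classification and severity".

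**Study cohort.** Section 9.8.1 lists infection, biopsy-proven rejection, biliary and vascular complications and reoperation, and introduces them with "These safety outcomes are data routinely collected in the registry immediately post-transplant". Strictures there must require surgical or radiological intervention. Sections 9.8.2 (month 3) and 9.8.3 (month 12) list rejection, biliary and vascular complications and reoperation again, now under "Safety outcomes that are not part of routine registry collection and will be collected for the study". At both times the stricture item reads "Both radiologically diagnosed and clinically apparent strictures". Section 9.8.3 describes the 12-month data as supplementing those of the inpatient stay.

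**Control cohort.** Section 10.1 takes all control outcomes from the registry, mirroring the study cohort where possible. Section 10.4.1 gives complications under "Inpatient Safety Outcomes as recorded in the registry": infection, biliary (including "Biliary tract strictures requiring intervention") and vascular. Its month 3 outcomes are survival and the lifestyle score. The month 12 list in 10.4.2 has no biliary, vascular, rejection or reoperation item; the nearest entry is "Number of readmissions in past 12 months (and reasons for readmission").

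**The concern.** The stated assessment times and the stated control data do not fit together. A 12-month complication rate is promised for both cohorts, but the control data stop at the inpatient stay. In the study cohort, follow-up for the same outcomes runs to 12 months, and the stricture definition loosens after the inpatient stage.

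Both differences act in one direction: they add events to the NMP column and none to the control column. The primary endpoint is meant to show that extra transplants are not bought with worse outcomes, so complications will be read closely alongside it. An apparent excess of biliary or vascular complications produced by follow-up alone would weaken that reading without cause.

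Two smaller faults belong to the same point. Rejection and reoperation are promised for both cohorts but are not in the control list. The by-severity summary needs grades that controls do not have.

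**Working it through.** The protocol states no safety rate or power for this comparison, so there is no figure to reproduce. The check is a comparison of sections, followed by the algebra of unequal ascertainment.

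**Step 1: what each cohort has, by 6.2 outcome**

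| Outcome | Study, inpatient (9.8.1) | Study, months 3 and 12 (9.8.2, 9.8.3) | Control, inpatient (10.4.1) | Control, months 3 and 12 (10.4.1, 10.4.2) |
|---|---|---|---|---|
| Infection | registry | none listed | registry | none |
| Biliary stricture | registry, intervention required | non-registry, intervention not required | registry, intervention required | none |
| Bile leak | registry | non-registry | registry | none |
| Vascular | registry | non-registry | registry | none |
| Biopsy-proven rejection | registry | non-registry | not listed | none |
| Reoperation | registry | non-registry | not listed | none |
| Clavien-Dindo grade | SAEs only | SAEs only | none | none |

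**Step 2: what follows**

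- Infection, biliary and vascular complications match in source and window at the inpatient stage, and strictures match in definition there. Compared on those items alone, the cohorts are ascertained alike.
- Biliary and vascular items differ in window once month 3 and 12 events are added. Strictures then differ in definition as well.
- Rejection and reoperation cannot be compared from the control list as written, although 9.8.1 places both in the registry.
- A severity summary by arm is impossible. Section 6.2 limits Clavien-Dindo grading to study-cohort SAEs.

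**Step 3: direction and dependence of the bias if later events are included**

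Let p be the true 12-month risk of an intervention-requiring stricture, equal in both cohorts. Let f be the share of those events that the inpatient registry items record. Let w be the factor by which the wider definition raises the study-cohort count (w = 1 if it adds nothing). Neither f nor w is in the document.

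- Control rate = p × f. Study rate = p × w. Apparent ratio = w / f, which does not depend on p.
- w = 1: f = 0.75 gives 1/0.75 = 1.33; f = 0.50 gives 2.0; f = 0.25 gives 4.0.
- w = 1.25: 1.25/0.75 = 1.67; 1.25/0.50 = 2.5; 1.25/0.25 = 5.0.
- Inpatient registry items in both cohorts: (p × f)/(p × f) = 1.0.

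For an absolute scale, take p = 10% from the anastomotic stricture figure in 12.2. With w = 1 the false difference is 10% × (1 − f), which is 2.5, 5.0 and 7.5 percentage points at the three values of f. That is an illustration only: 12.2 attaches neither a time window nor a stricture definition to the 10%.

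**The case against.** The best defence is that nothing orders the unequal comparison. A matched inpatient registry set exists for infection, biliary and vascular items. Section 6.2 keeps the intervention-requiring definition for both cohorts. Sections 9.8.2 and 9.8.3 say most data come from the registry precisely so that the cohorts are comparable. Section 14.4 recognises that some outcomes are captured only on study-cohort eCRFs, and 13.2 says outcomes measured only in the study arm will be described. Month 3 and 12 complications can be read as belonging to that group. Section 10.1 leaves the registry fields to a separate data-sources document, and the SAP may settle the window.

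Most of this stands, and it limits the point. A reader might infer that the planned safety comparison is biased as it stands, with NMP complications inflated several-fold and to a nominally significant degree. The documents do not support that. It needs a pooling step that no section prescribes and an inpatient share that no section gives. It also needs a safety test, and 13.2 names only a summary.

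The defence does not remove the conflict. The synopsis timepoints cover both cohorts through month 12. Section 13.2 compares all secondary outcomes without restriction. Calling the 12-month data a supplement to the inpatient data invites adding the two together. Biliary and vascular complications are measured in both cohorts, so the rule for study-only outcomes does not plainly apply to them. The missing control items and grades are differences within the protocol itself.

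**Conclusion.** The mismatch is established from the text: the synopsis, 6.2 and 13.2 promise a by-arm assessment of adverse outcomes through month 12 that the control data in 10.4 cannot support like for like. The bias is conditional. It arises if the study cohort's month 3 and 12 events enter the by-arm summary, and it then runs against NMP. Its size cannot be derived from the document; the ratios of 1.33 to 5.0 above only show how it depends on the assumed f and w. On the matched inpatient items, with equal true risks, the expected ratio is 1.0.

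Two findings need no assumption. Rejection and reoperation are absent from the control list although 9.8.1 says the registry holds them, and severity cannot be summarised for controls. The point deserves correction before analysis. It does not touch functional utilisation, the primary endpoint.

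**What to change.** - In the synopsis, 6.2 and 13.2, limit the between-cohort comparison of adverse outcomes to the common inpatient registry items, with strictures requiring intervention in both cohorts. Change the synopsis timepoints for the safety objective to match.
- In 10.4.1, add biopsy-proven rejection and reoperation to the control extraction from the registry.
- In 13.2, state that month 3 and month 12 complications, the wider stricture definition and Clavien-Dindo grades are reported descriptively for the study cohort only, with no control column. Remove severity from the by-arm summary.

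The cost is wording plus two registry fields for a retrospective cohort. The real loss is that no comparative 12-month complication rate will be available. Readmissions with reasons, which 9.8.3 and 10.4.2 take from the registry for both cohorts at month 12, remain as an indirect later measure but do not replace such a rate.
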